##### **4.1.3.2. Dose reduction/drug discontinuation scheme for afatinib**

In the event of treatment-related toxicities, the treatment with afatinib should be handled according to the schedule in Table 4.1.3.2:1.

**Table 4.1.3.2:1 Dose reduction/dose discontinuation scheme**

AE Type and grade	Action	Dose reduction/ discontinuation scheme
Grade 4 rash	Permanently discontinue afatinib	Permanently discontinue afatinib
Grade $\geq 3$ interstitial lung disease	Permanently discontinue afatinib	Permanently discontinue afatinib
Grade 4 hepatic impairment	Permanently discontinue afatinib	Permanently discontinue afatinib
Grade $\geq 3$ keratitis	Permanently discontinue afatinib	Permanently discontinue afatinib
Grade 2 left ventricular dysfunction (i.e., new resting ejection fraction of 40-50%; OR a 10-19% drop from baseline) 	Pause treatment with afatinib for 14 days and then repeat MUGA scan. If the ejection fraction has resolved to grade 1 or better at the time of the repeat MUGA, study drug will be resumed. If the toxicity has not resolved, afatinib should be permanently discontinued.	If patient was receiving 40 mg, resume treatment at 30 mg  . If patient was receiving 30 mg, resume treatment at 20 mg  . If patient was receiving 20 mg, discontinue afatinib.
Any symptomatic (grade $\geq 3$ ) left ventricular dysfunction 	Permanently discontinue afatinib	Permanently discontinue afatinib
CTCAE grade $\geq 2$ diarrhea persisting for 2 or more consecutive days (48 hours) despite adequate anti-diarrheal medication/hydration	Pause treatment with afatinib until toxicity has recovered to CTCAE grade $\leq 1$ or baseline  . If patient has not recovered to CTCAE grade $\leq 1$ within 14 days, study treatment should be permanently discontinued 	If patient was receiving 40 mg, resume treatment at 30 mg  . If patient was receiving 30 mg, resume treatment at 20 mg  . If patient was receiving 20 mg, discontinue afatinib.
CTCAE grade $\geq 2$ nausea and/or vomiting persisting for 3 or more consecutive days despite anti-emetic treatment/hydration		
CTCAE grade 2 or grade 3 worsening of renal function as measured by serum creatinine, newly developed proteinuria, or newly developed decrease in glomerular filtration rate of more than 50% from baseline		
CTCAE grade 4 worsening of renal function	Permanently discontinue afatinib	Permanently discontinue afatinib
Any other drug related AE CTCAE grade $\geq 3$	Pause treatment with afatinib until toxicity has recovered to CTCAE grade $\leq 1$ or baseline  . If patient has not recovered to CTCAE grade $\leq 1$ within 14 days, study treatment should be permanently discontinued 	If patient was receiving 40 mg, resume treatment at 30 mg  . If patient was receiving 30 mg, resume treatment at 20 mg  . If patient was receiving 20 mg, discontinue afatinib.

 Baseline is defined as the CTCAE grade until start of treatment In the event that the patient is deriving obvious clinical benefit in the opinion of the investigator, but has not recovered within 14 days, the further treatment of the patient will be decided by the lead PI who may consult with the appropriate individuals at BI. Once a dose reduction is applied, the reduced dose is maintained unless further dose reduction is needed. Defined according to CTCAE version 4.0, page 109, adverse event denoted as “ejection fraction decreased”

 Defined according to CTCAE version 4.0, page 9, adverse event denoted as “left ventricular systolic dysfunction”

Dose reduction should always follow a treatment pause. In the event of a treatment pause, subsequent visits/courses should not be delayed.

In the event of a prolonged ( $\geq 7$  consecutive days) Grade 2 drug-related event not listed in Table 4.1.3.2:1, which is poorly tolerated by the patient, the treating investigator may choose to pause the medication for up to 14 days to allow the patient to recover followed by a dose reduction according to the schedule in Table 4.1.3.2:1.

In the event of any unrelated adverse events or unrelated serious adverse events, the treating investigator may choose to pause the medication for up to 7 days to allow the patient to recover, but no dose reduction should occur. If the treating investigator chooses to pause the medication for more than 7 days and believes that the patient would derive clinical benefit from continuing medication, the decision to continue medication will be made by the lead investigator who may consult with BI’s medical monitor.

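### A deep, symptom-free ejection-fraction fall meets neither left-ventricular row of the dose table and defaults to a looser catch-all row

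*Combined protocol and SAP*

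**What the plan says.** Section 4.1.3.2 sends treatment-related toxicities to Table 4.1.3.2:1. Three of its rows matter here.

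- **Grade 2 left ventricular row.** The trigger is "new resting ejection fraction of 40-50%; OR a 10-19% drop from baseline", which footnote 4 ties to the CTCAE 4.0 term for decreased ejection fraction. The action is "Pause treatment with afatinib for 14 days and then repeat MUGA scan". If the value is back to grade 1 or better, treatment resumes one dose level lower. Otherwise: "If the toxicity has not resolved, afatinib should be permanently discontinued". The row carries no footnote 2 marker.
- **Second left ventricular row.** Its trigger starts "Any symptomatic (grade" and continues with 3 or higher. Footnote 5 ties it to a different CTCAE term ("Defined according to CTCAE version 4.0, page 9, adverse event denoted as" left ventricular systolic dysfunction). The action is permanent discontinuation.
- **Last row.** Its trigger starts "Any other drug related AE CTCAE grade" and again continues with 3 or higher. The drug is held until the event is back to grade 1 or less, or to baseline. Failing recovery "within 14 days, study treatment should be permanently discontinued", subject to footnote 2. Under that footnote, if the investigator sees obvious clinical benefit, "the further treatment of the patient will be decided by the lead PI who may consult with the appropriate individuals at BI".

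Outside the table, Section 5.2.4.2 refers MUGA assessment to the Flow Chart, which has a scan at screening and every 12 weeks on therapy.

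**The concern.** Both limbs of the grade 2 definition have a worst-case limit, and the only more severe cardiac row is restricted to symptomatic patients. A large fall in ejection fraction without symptoms therefore appears to have no cardiac rule and to land in the catch-all row.

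Two things are at stake. First, recovery of a symptom-free fall cannot be seen without imaging, and the catch-all row neither names nor times a scan. Patients with the more severe silent fall are then the ones who could stay on afatinib without documented recovery. Second, a site that takes the grade in parentheses in the second cardiac row to cover every fall of that grade would stop the drug permanently, while a site that follows the word symptomatic would pause and might resume. Management would differ between sites for the same finding.

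**Working it through.** The plan states no figure on this point, so there is none to reproduce. The check treats the table as a decision rule.

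**Inputs.** The trigger limits and actions come from Table 4.1.3.2:1 and its footnotes. Section 3.3.2 sets no minimum ejection fraction for entry, so baselines of 50% to 70% are assumed. The documents do not print whether a drop means percentage points or relative percent, so both are shown.

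**Step 1: where the grade 2 row ends.** Let B be baseline and E the on-treatment ejection fraction. The drop is d = B − E in points, or d = 100 × (B − E)/B in relative percent. The row applies if 40 ≤ E ≤ 50 or 10 ≤ d < 20 (the printed 19 is taken as running up to 20). A value below 40% is outside both limbs when d ≥ 20, which means:

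- points: E < 40 and E ≤ B − 20
- relative: E < 40 and E ≤ 0.8 × B

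| Baseline B | B − 20 | Gap starts (points) | 0.8 × B | Gap starts (relative) |
|---|---|---|---|---|
| 50 | 30 | 30 or less | 40 | below 40 |
| 55 | 35 | 35 or less | 44 | below 40 |
| 60 | 40 | below 40 | 48 | below 40 |
| 65 | 45 | below 40 | 52 | below 40 |
| 70 | 50 | below 40 | 56 | below 40 |

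Worked cases:

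- 60% to 35%: 60 − 35 = 25 points; 25/60 = 41.7% relative. In neither limb on either reading.
- 70% to 45%: 25 points, but 45 lies within 40–50. Covered.
- 52% to 38%: 52 − 38 = 14 points, so covered if points; 14/52 = 26.9%, so not covered if relative.

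On the relative reading a high baseline also leaves a small band above 50% uncovered: 70% to 55% is 15/70 = 21.4%. That band is left aside here.

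**Step 2: which row takes the 60% to 35% case.** It is worse than the printed grade 2 range of the same graded term, so it is inferred to be grade 3 or worse; the grade 3 range itself is not printed. Without symptoms it does not meet the second cardiac row, whose footnote also points to another CTCAE term. If drug-related, the last row is the only one left.

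**Step 3: the two rules side by side.**

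| | Grade 2 cardiac row | Last row |
|---|---|---|
| Pause | fixed, 14 days | until recovery |
| Repeat MUGA | required | not named |
| Not recovered | permanent stop, no exception | stop at 14 days, unless footnote 2 is used |
| Dose on resuming | 40 to 30 mg, 30 to 20 mg, stop at 20 mg | same |

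Dose steps and the default stop match. The other differences make the last row less specific, and it is the row that takes the deeper fall. If no extra scan is ordered, the next scheduled one may be up to 12 weeks away.

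**The case against.** The strongest reply is that the event is still managed. The last row pauses the drug, makes resumption depend on recovery, lowers the dose and stops by default at 14 days. Recovery of an ejection-fraction value can only be judged by measuring it, and Section 5.2.4.2 names MUGA as the method, so a careful site would re-image. This largely stands in practice. Even so, the row neither requires nor times the scan, although the authors did so for the milder fall.

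Footnote 2 is also narrow. It needs obvious benefit, refers the decision to the lead investigator, and does not say that treatment must continue. That is true, but the grade 2 row allows no such route, so the ordering is still reversed.

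A third reply is that the two cardiac rows run in sequence and the second was meant to catch everything above grade 2. That may have been the intent. The word symptomatic and the different CTCAE term in footnote 5 read against it, and if it was the intent, the text still needs correcting.

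Other safeguards exist: removal for unacceptable adverse events (Section 3.3.4), recording of clinically relevant MUGA changes (Section 5.2.2.1), 12-weekly scans, and weekly safety review (Section 8.1). They make unmonitored continuation less likely, but none sets a rule for this event.

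The frequency is unknown. The first-cohort patient who stopped for depressed ejection fraction had not progressed, and treatment was in fact stopped. That case shows only that the toxicity occurs, not that a patient was kept on drug.

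**Conclusion.** The concern holds. As written, a drug-related, asymptomatic fall to below 40% that is also a drop of 20 or more meets neither cardiac row. It is handled by a row with no named MUGA, no fixed pause and an exception that the grade 2 row lacks.

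The conclusion rests on the event being grade 3 or worse, which is inferred from the printed grade 2 range, and on reading symptomatic literally. The thresholds depend on the assumed baselines and on the meaning of drop; the 60% to 35% example does not. The number of patients affected cannot be estimated from the documents. The only related figure is 1 of 23 (1/23 = 4.3%) stopping for depressed ejection fraction, with grade and symptoms not given.

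This is a safety-management gap. Sample size, stopping boundaries and the 6-month PFS analysis are not affected.

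**What to change.** At the next amendment, add drug-related decreased ejection fraction of grade 3 or worse, regardless of symptoms, to a left ventricular row of Table 4.1.3.2:1. Apply at least the grade 2 rules: a 14-day pause, a mandatory repeat MUGA, permanent discontinuation unless resolved to grade 1 or better, and footnote 2 stated not to apply. The sponsor may prefer immediate permanent discontinuation; either choice removes the conflict between the two readings. The same edit could state whether a drop is in percentage points or relative percent. Grade 1 falls and falls judged unrelated to the drug can stay as they are.

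The cost is one table row. The downside is that a rare patient who is benefiting loses the footnote 2 exception, as already happens at grade 2.

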#### **4.1.4 Packaging, labelling, and storage**

Medication numbers will be unique to each bottle and will be used for tracking purposes only.

##### **4.1.4.1 Afatinib dispensing**

Afatinib will be supplied as film-coated tablets. Available dosage strengths will be 40, 30, and 20 mg. Tablets will be supplied in HDPE, child-resistant, tamper-evident bottles.

Bottles/boxes will be labelled according to local regulations and will include the following as a minimum;

- Study number (13-0540/ 1200.171)
- Product name: afatinib
- Contents of the bottle (30 tablets)
- Tablet strength (mg)
- Batch number
- Medication number
- Use-by date
- Storage information
- Instructions for use
- Sponsor name and address
- A statement that the medication is for clinical study use only
- A caution statement

Since pill bottles contain #30 tablets, patients will be given two pill bottles on day 1 of the first cycle (to have adequate supply to complete the entire cycle), and two bottles on day 1 of each subsequent cycle. All patients will start with 40 mg tablets and in the event that dose reduction is necessary, the patient will return to the clinic and new medication will be dispensed.

#### **4.1.4.2 Storage conditions**

Afatinib must be stored in the original packaging. Film-coated tablets are humidity and light sensitive and therefore bottles must be kept tightly closed. Tablets will be stored at the study site in a limited access area and must be stored in accordance with the instructions on the label.

#### **4.1.5 Drug accountability**

Drug supplies, which will be provided to the study sites by Boehringer Ingelheim, will be kept in a secure, limited access storage area under the storage conditions. Where necessary, a temperature log must be maintained to make certain that the drug supplies are stored at the correct temperature.

The responsible person must maintain records of the product's delivery to the study site, the inventory at the site, the use by each patient, and the return to the Boehringer Ingelheim or alternative disposition of unused product(s).

These records will include dates, quantities, batch/serial numbers, expiry ('use by') dates, and the unique code numbers assigned to the investigational product(s) and study patients. The responsible person will maintain records that document adequately that the patients were provided the doses specified and reconcile all investigational product(s) received from Boehringer Ingelheim. The responsible person must verify that all unused or partially used drug supplies have been returned by the clinical study patient.

## **4.2 CONCOMITANT THERAPY, RESTRICTIONS, PRECAUTIONS, AND RESCUE TREATMENT**

### **4.2.1 Rescue medication, emergency procedures, and additional treatment(s)**

Rescue medications to reverse the actions of afatinib are not available. Side effects of these treatments should be treated symptomatically. Growth factor support will be used following ASCO Guidelines.

The current version of the investigator brochure lists the AEs expected with afatinib. Suggested treatments for diarrhea, nausea, vomiting and rash/acne are described in Section 4.2.3.

During study participation symptomatic treatment of tumor associated symptoms is allowed. Treatment with corticosteroids is allowed. Concomitant medications or therapy to provide adequate care may be given as clinically necessary. All concomitant (non-oncological) medications which are taken between study informed consent and the first follow-up visit should be recorded in the case report form (CRF) with the start and end of treatment dates, the total daily dose, the respective unit and the reason for use.

**Careful assessment of all patients with an acute onset and/or unexplained worsening of pulmonary symptoms (dyspnea, cough, fever) should be performed to exclude ILD. Study drug should be interrupted pending investigation of these symptoms. If interstitial lung disease is diagnosed, study drug should be permanently discontinued and appropriate treatment instituted as necessary.**

### **4.2.2 Restrictions**

#### **4.2.2.1 Restrictions regarding concomitant treatment**

Patients may not receive any other anti-cancer treatments while on study (bone-directed supportive therapies such as bisphosphonates or RANKL inhibitors are permitted). Patients cannot have received another anti-cancer chemotherapy or immunotherapy or investigational agent within 2 weeks prior to the first dose of study treatment, and cannot have received radiotherapy within 4 weeks prior to the first dose of study treatment.

#### **4.2.2.2 Restrictions on diet and life style**

##### **For afatinib:**

Afatinib should be taken without food (i.e. afatinib should be taken at least 1 hour before or at least 2 hours after a meal).

In the event of diarrhea, patients should be advised to avoid lactose-containing products or any foods known to aggravate diarrhea.

To prevent skin related adverse events it is currently proactively recommended to avoid intense irradiation with UV light, e.g. sunbathing or visiting a solarium, and to use strict sun

protection during the treatment period of the study. In case of sun exposure a sunscreen of Sun Protection Factor 15 (SPF 15) or higher, preferably containing zinc oxide, should be used, preferably a thick, alcohol-free emollient cream. Harsh detergents should be avoided.

#### **4.2.2.3 Precautions**

Keratitis is a known adverse event associated with afatinib, and it should be used with caution in patients with a known history of keratitis, ulcerative keratitis, or severe dry eye. Although contact lens use is a risk factor for keratitis and ulceration, the use of contact lenses will not preclude patient enrollment to this study.

### **4.2.3 Concomitant therapy**

#### **4.2.3.1 Management of diarrhea following treatment with afatinib**

Close monitoring and proactive management of diarrhea is essential for successful treatment of patients with afatinib. Early and appropriate intervention can prevent the development of more severe diarrhea. In most cases, loperamide controls diarrhea caused by afatinib.

Loperamide should be available at the start of therapy and kept with the patient at all times; it is therefore advisable that patients be given a prescription at the time of initiating treatment with afatinib.

The recommendations for management are as follows (see also Section 4.2.2.2):

- If any diarrhea is experienced (CTCAE Grade 1), two 2 mg loperamide tablets should be taken immediately, followed by one 2 mg tablet with every loose bowel movement, up to a maximum daily dose of 10 tablets (20 mg).
- Oral hydration is essential regardless of severity; appropriate rehydration (1.5 L/m^2/day plus equivalent of actual fluid loss) and electrolyte replacement has to be ensured in the event of CTCAE Grade 2 and Grade 3 adverse events.
- For CTCAE Grade  $\geq 2$  diarrhea lasting  $\geq 2$  days (48 hours) despite adequate antidiarrheal treatment, afatinib must be paused until recovery to CTCAE  $\leq$  Grade 1. Upon recovery, afatinib should be resumed at a reduced dose according to the dose reduction scheme outlined in Section 4.1.3.2.

The occurrence of diarrhea and the outcome of treatment will be recorded in the AE section of the CRF.

If despite optimal supportive care and a treatment pause diarrhea does not resolve to CTC Grade  $\leq 1$  within 14 days, the patient must not receive any further afatinib treatment.

#### 4.2.3.2 Management of nausea and vomiting following treatment with afatinib

Nausea and vomiting may significantly affect patients' adherence to the treatment and their quality of life. In order to reduce the occurrence and the intensity of emesis, the patients should be treated according to the recommendation given in Table 4.2.3.2:1.

**Table 4.2.3.2: 1 Management of nausea and vomiting**

CTCAE Grade	Antiemetic treatment
Nausea = grade 0 and Vomiting = grade 0	No antiemetic prophylactic treatment
Nausea = grade 1 and Vomiting = grade 0	Antiemetic treatment if deemed necessary by the investigator
Nausea = grade 2 and Vomiting = grade 0	Antiemetic treatment 
Nausea = grade 0, 1 or 2 and Vomiting = grade 1 or 2	Pause afatinib treatment if grade 2 vomiting or grade 2 nausea persists for 3 or more consecutive days despite optimal supportive care. Resume treatment when CTCAE grade $\leq$ 1.
Vomiting $\geq$ grade 3 or Nausea $\geq$ grade 3	Antiemetic treatment   Pause afatinib treatment until return to CTCAE grade $\leq$ 1 or baseline  .

1 Antiemetic treatment should follow the recommendations given in the Consensus Statement of the Antiemetic Subcommittee of the Multinational Association of Supportive Care in Cancer (MASCC): Prevention of chemotherapy- and radiotherapy-induced emesis: Results of the Perugia Consensus Conference (R06-0986).

2 Baseline is defined as the CTCAE grade at the start of treatment.

After a treatment pause the dose of afatinib should be reduced according to the dose reduction scheme in Table 4.1.3.2:1.

The occurrence of nausea and/or vomiting and the outcome of treatment will be recorded in the AE section of the CRF.

In case of nausea and/or vomiting  $\geq$  CTCAE grade 2, appropriate hydration (1.5 L/m^2/day plus hydration deficit) must be ensured.

#### 4.2.3.3 Management of rash following treatment with afatinib

A proactive and early approach to management of rash is crucial. Rash can be managed by a variety of treatment options to relieve symptoms and to reduce the rash.

The recommendations for management are as follows:

- General/Prevention: see Section 4.2.2.2
- CTCAE Grade 1 rash: mild rash may not need treatment. However, if treatment is considered necessary, topical hydrocortisone (1% or 2.5%) cream and/or clindamycin 1% gel can be used.
- CTCAE Grade 2 rash: relief from major symptoms caused by CTCAE Grade 2 skin-related adverse events should be achieved by a combination of local and systemic therapies including:
  - Systemic antibiotics (e.g. doxycycline or minocycline, etc.).
  - Topical treatment (e.g. hydrocortisone 2.5% cream, clindamycin 1% gel, pimecrolimus 1% cream)

and / or

- Antihistamines (e.g. diphenhydramine, etc.)

- Oral corticosteroid (low dose and short term, i.e. < 10 days treatment) may be added at the investigator's discretion.
  - Systemic and topical treatment should be initiated at the start of CTCAE Grade 2 rash and continued until improvement or resolution to CTCAE Grade  $\leq 1$ . If grade 2 rash persists for  $\geq 7$  days despite treatment and is poorly tolerated by the patient, the investigator may choose to pause treatment for up to 14 days followed by a reduction in the dose of afatinib according to the dose reduction scheme in Table 4.1.3.2: 1.
- CTCAE Grade 3 rash: may be treated in a manner similar to CTCAE Grade 2 rash. In the event of CTCAE Grade 3 rash, treatment with afatinib should be paused until recovery to CTCAE Grade  $\leq 1$ . Treatment should be resumed at a reduced dose (see Section 4.1.3.2). If CTCAE Grade 3 rash does not resolve to CTCAE Grade  $\leq 1$  within 14 days of stopping afatinib treatment and despite optimal supportive care, the patient should not receive any further treatment with afatinib.
- CTCAE grade 4 rash: permanently discontinue afatinib. Treatment should be in a manner similar to CTCAE Grade 2/3 rash

